## 1.7 Study Rationale

As homozygosity for *HSD3B1*(1245C) SNP can impact response and mediate resistance to ADT, evaluating the effect of such genotype variation on the level of steroid metabolites and the intratumoral DHT concentration in benign and tumor tissue of men receiving a short course of Apalutamide and leuprolide prior to undergo RP is of interest. We hypothesize that patients with homozygous *HSD3B1* (1245C) inheritance that leads to a gain of function in  $3\beta$ HSD1, will have a sustained androgen synthesis from extragonadal precursor steroids and higher concentrations of DHT compared to wild-type *HSD3B1* (1245A) inheritance in the context of castration. Also, we expect intermediate levels of DHT in the heterozygous *HSD3B1* (1245C) group. We also hypothesize that Apalutamide will reverse the effects of elevated DHT on AR signaling in prostate tissue. For example, although DHT concentrations will be higher in the *HSD3B1* (1245C) groups, PSA expression will be equivalent among all groups. We anticipate that these studies will serve as the first step in identifying patients with prostate cancer who will benefit from upfront treatment with Apalutamide in addition to medical castration.

## 2 Objectives

### 2.1 Primary Objective

To evaluate the differential effect of neo-adjuvant leuprolide and Apalutamide on dihydrotestosterone (DHT) concentration in benign prostate tissue based on *HSD3B1* genotype.

### 2.2 Secondary Objectives

2.2.1 To evaluate the differential effect of neoadjuvant leuprolide and Apalutamide on other androgen (testosterone (T), dehydroepiandrosterone (DHEA), androstenediol, 5 $\alpha$ -androstenedione (5 $\alpha$ -dione), androstenedione (AD), androsterone and 5 $\alpha$ -androstenediol) concentrations in benign and malignant prostate tissue based on *HSD3B1* genotype.

2.2.2 To compare the level of DHT, T, DHEA, androstenediol, 5 $\alpha$ -dione, AD, androsterone and 5 $\alpha$ -androstenediol between normal and malignant prostate tissue after neoadjuvant treatment with leuprolide and Apalutamide

2.2.3 To determine the safety of the combination of Leuprolide and Apalutamide administered prior to radical prostatectomy

[figure not shown]
2.2.4 To evaluate PSA, FKBP5, TMPRSS2, EZH2, H3K27 and UBE2C tissue expression (via IHC and qPCR) in benign and malignant prostate tissue after treatment with Leuprolide and Apalutamide and Apalutamide.

### 3 Study design

#### 3.1 Summary

The primary goal of the study is to evaluate the differential effect of neo-adjuvant Apalutamide and leuprolide on dihydrotestosterone (DHT) concentration in benign prostate tissue based on *HSD3B1* genotype. Newly diagnosed, biopsy-proven, intermediate or high-risk prostate cancer patients (G 4+3 or higher,  $\geq$ T2b, PSA  $\geq$  10), who are candidates for radical prostatectomy (RP) are eligible to participate in this study. In order to have enough tumor tissue to perform all of the tests, a minimum tissue requirement of  $\geq$ 1 positive core biopsy. All participating patients will receive a single dose of leuprolide 7.5 mg IM in addition to Apalutamide 240 mg orally daily for four weeks prior to RP. Treatment will be started on day  $(-28) \pm 3$  from the scheduled RP date to minimize the variability of treatment duration. Apalutamide will be continued up to and including the day before radical prostatectomy. Although pre-treatment MRIs of the prostate will be ideal, this protocol does not mandate these imaging studies for study enrollment. Of note, the vast majority of patients undergoing RP at our institutions undergo MRI of prostate for further staging purposes. Thus, the vast majority of our patients will have this completed. Blood will be drawn at baseline and on the day of surgery to evaluate serum PSA and androgen metabolite levels. After RP, fresh tissue from the surgical specimen will be sampled by the GU pathologist (multiple punch biopsies to increase the chance of capturing benign and tumor tissue) with the same methodology that we have previously described. All steroids will be extracted from prostate tissue (20 mg), derivatized by the Girard-T oxime methodology to increase sensitivity, and quantitated by mass spectrometry, as previously described. Expression of PSA transcript and protein will be assessed as we have performed routinely and described previously. Levels of DHT, T, DHEA, androstenediol, 5 $\alpha$ -dione, AD, androsterone, and 5 $\alpha$ -androstane-3 $\beta$ -diol will be measured in all specimens. The underlying hypothesis is that under a recessive model, homozygous *HSD3B1* (1245C) is stabilizing and leads to a gain of function in 3 $\beta$ HSD1 that ultimately results in sustained androgen synthesis compared to wild-type *HSD3B1* (1245A), after treatment with leuprolide. We expect to have intermediate levels of these metabolites in the heterozygous *HSD3B1* (1245C) group.

### 3.2 Study Schema

## 4 Study Population

### 4.1 Inclusion criteria

- 4.1.1 Male  $\geq$  18 years of age
- 4.1.2 Adenocarcinoma of the prostate with histological or cytological confirmation without neuroendocrine differentiation or small cell histology and with any one of the following: G 4+3 or higher or PSA  $\geq$  10 or  $\geq$ T2b, for whom radical prostatectomy has been recommended and who choose to undergo radical prostatectomy.
- 4.1.3 A minimum tissue requirement of  $\geq$ 1 core biopsy with tumor involvement.
- 4.1.4 Have an Eastern Cooperative Oncology Group (ECOG) performance status 0 or 1
- 4.1.5 Hemoglobin of  $\geq$  10 g/dL, independent of transfusion and/or growth factors within 3 months prior to randomization
- 4.1.6 Platelet count of  $\geq$  100k/mL independent of transfusion and/or growth factors within 3 months prior to randomization
- 4.1.7 Serum albumin  $\geq$ 3.0 g/dL
- 4.1.8 Serum creatinine  $<$  2.0 times the upper limit of normal (ULN) {or a calculated creatinine clearance  $\geq$  60 mL/min}
- 4.1.9 Serum potassium  $\geq$ 3.5 mmol/L
- 4.1.10 Aspartate aminotransferase (AST) and alanine aminotransferase (ALT)  $<$  2.5 x ULN
- 4.1.11 Total serum bilirubin levels  $<$  1.5 x ULN (Note: In subjects with Gilbert's syndrome, if total bilirubin is  $>$ 1.5 x ULN, measure direct and indirect bilirubin and if direct bilirubin is  $\leq$ 1.5 x ULN, subject may be eligible)
- 4.1.12 Be capable of swallowing study agents whole as a tablet
- 4.1.13 Be willing/able to adhere to the prohibitions and restrictions specified in this protocol
- 4.1.14 Have signed an informed consent document indicating that the subject understands the purpose of and procedures required for the study and are willing to participate in the study.
- 4.1.15 Medications known to lower the seizure threshold (see list under prohibited meds) must be discontinued or substituted at least 4 weeks prior to study entry.
- 4.1.16 Agrees to use a condom (even men with vasectomies) and another effective method of birth control if he is having sex with a woman of childbearing potential or agrees to use a condom if he is having sex with a woman who is pregnant while on study drug and for 3 months following the last dose of study drug. Must also agree not to donate sperm during the study and for 3 months following the last dose of study drug.

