4.2.9 Have a known history of pituitary or adrenal dysfunction

4.2.10 Have clinically significant heart disease as evidenced by severe or unstable angina, myocardial infarction, symptomatic congestive heart failure, arterial or venous thromboembolic

events (e.g., pulmonary embolism, cerebrovascular accident including transient ischemic attacks), or clinically significant ventricular arrhythmias within 6 months prior to randomization

4.2.11 Have a history of gastric bypass surgery or severe malabsorption that may interfere with the absorption of the study agents

4.2.12 Be taking or require the use of prohibited medications as listed in Section 6.3.2.1

4.2.13 Have any condition that, in the opinion of the investigator, would compromise the well-being of the subject or the study or prevent the subject from meeting or performing study requirements

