## 5.2 Pre-treatment Evaluation

Clinical: required on Cycle 1 Day (-28) or within 28 days before the treatment initiation

- 5.2.1 History and physical examination, including height, weight, and vital signs
- 5.2.2 Performance status evaluation
- 5.2.3 Laboratory /Diagnostic: required within 28 days before the treatment initiation.
  - 5.2.3.1 CBC, platelet count and differential
  - 5.2.3.2 Serum chemistries: includes BUN, Creatinine, ALT, and AST, glucose, alkaline phosphatase, total bilirubin, TSH and LDH. If TSH is abnormal a T3 and T4 level will be required.
  - 5.2.3.3 Testosterone, DHEA, DHEA-S, and AD, Direct Renin and Aldosterone/Direct Renin Ratio serum level
  - 5.2.3.4 PSA
  - 5.2.3.5 Study blood draw for the measurement of serum steroids concentration
  - 5.2.3.6 Imaging/Diagnostic: will be performed at the discretion of the treating physician. Obtaining prostate MRI is preferred but not mandatory for the study enrollment.

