## 5.3 Registration process

To register a patient, the following documents should be completed by the research nurse and e-mailed to the Study Coordinator:

- Registration Form
  - Eligibility Worksheet
  - Copy of source documentation (required laboratory tests, radiographic scans (if applicable), physician notes, nursing notes, list of medications, pathology/surgical reports, etc.)
- Signed patient consent form to complete the registration process, the Coordinator will
- Verify patient eligibility worksheet is complete
  - Request additional documentation if necessary
  - Assign a patient study number
  - Register the patient on the study using the ONCORE database

- 6 E-mail a letter of Confirmation of Registration, including the patient study number, to the responsible research nurse treatment plan.

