#### 10.2.2 *HSD3B1* Genotyping by Melting Curve Assay

Genomic DNA will be prepared from peripheral blood using DNeasy Blood and Tissue Kit (QIAGEN, Germantown, MD). PCR products of the promoter region, all exons, exon-intron junctions and the

30-UTR will be sequenced to identify mutations in *HSD3B1*. To sequence the 30 flanking region of *HSD3B1*, primer set (Forward: 50-ATGTGGAGGGAGGTGTGAGT-30 and Reverse: 50-ACGGAGATGGGTCTCTTCCA-30 ) will be used with an annealing temperature of 62\_C. Genotyping PCR reaction (50 ml) will be done with 30-100 ng genomic DNA, 1 x PCR buffer with 0.2 mM dNTP, 0.2 mM of each primer, and 0.5 ml Phusion High-Fidelity DNA Polymerase (New England BioLabs Inc, Ipswich, MA). 1 mL purple top tube will be used for genotyping purposes at indicated time points.

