## 11 Study Calendar

**Table 2. Study Calendar**

	Eligibility screening	Cycle 1, Day (-28) e	Pre-op evaluation (1 to 3 days before surgery)		off Apalutamide follow-up visit in 4 -8 weeks after RP h
Leuprolide IM injection + Apalutamide distribution		X a		Prostatectomy  (Day of surgery) k	
Tissue Core Biopsy from Initial Diagnosis		X			
MRI Prostate b					
Informed consent		X			
Demographics		X			
Medical History		X	X		X
Prior and concomitant medication review c		X	X		X
Vital Signs		X	X		X
Height/Weight/BSA		X	X		X
Physical Exam		X	X		X
Performance Status		X	X		X
CBC/diff, platelets		X	X l		X
Serum chemistries d		X	X l		X
TSH l		X	X		X
PT/PTT		X	X l		
Genotyping Analysis	X e				
Evaluation of AE's		X	X	X	
PSA		X	X l		
Testosterone, DHEA, DHEA-S, Androstenedione, Direct Renin and Aldosterone/Direct Renin Ratio		X	X l		
Blood for Correlative Studies f	X			X	

a: Study agents include Apalutamide. Patients will receive these medications for the entire treatment course at Day (-28) ± 3 days up to and including the day before prostatectomy (day of surgery).

b: MRI of the prostate will be completed at the discretion of the treating Physician. Although this imaging technique is routinely done at the Cleveland clinic prior to patients undergoing RP, it will be desired but not be mandatory for study entry.

c: Refer to Section 7.3 for further details on reporting prior and concomitant medications.

d: Sodium, potassium, chloride, CO2, BUN, Creatinine, Glucose, LFT's (AST/ALT/Alkaline Phosphatase, Albumin, LDH, total bilirubin), and Calcium. Testosterone, PSA, DHEA, DHEA-S and

AD levels will be measured within 28 days of treatment initiation and at the end of C1 of therapy as above.

e: Blood will be drawn for *HSD3B1* genotyping for the research laboratory.

f: Blood draw for steroid concentration in the serum and to understand how tumors use and make hormones. This sample will be sent to [name] lab.

g: Laboratory tests and procedures must be completed on Cycle 1 Day (-28) or within 28 days prior to the start of study agents Leuprolide IM injection and Apalutamide distribution.

h: Post-operative follow up visit will ideally occur between 4 and 8 weeks after surgery. Time line may vary in order to coordinate with Urology follow up visit.

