I: Allowable window for lab collection is 1-3 days prior to, or on, the day of prostatectomy.

J: Allowable window for lab collection is 1-7 days prior to prostatectomy.

K: Must be completed within 28 days  $\pm 3$  from the start of Leuprolide IM injection and Apalutamide distribution.

L: Thyroid stimulating hormone (TSH) should be evaluated throughout the study (with T3 and T4 done only if TSH is abnormal) as follows: On Cycle 1 or within 28 days before treatment initiation, at the end of Cycle 1 (approximately day 28 Pre-op evaluation), and 4-8 weeks after RP (Follow Up evaluation).

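### As supplied, inclusion criterion 4.1.6 sets the platelet minimum per millilitre, 1,000 times below the presumably intended 100,000 per microlitre; confirm and correct the unit

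*Combined protocol and SAP*

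**What the plan says.** Section 4.1.6 (Inclusion criteria) gives the platelet minimum as "100k/mL independent of transfusion and/or growth factors", with a three-month look-back for the transfusion and growth-factor condition. This is the only platelet limit in the combined protocol and SAP.

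Platelets appear elsewhere only as a test to be done:

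- Section 5.2.3.1 (Pre-treatment Evaluation) lists "CBC, platelet count and differential", with no limit and no unit.
- The Study Calendar in Section 11 has a row "CBC/diff, platelets" at baseline, at the pre-operative evaluation and at follow-up, again with no limit. A calendar footnote on timing before surgery reads "Allowable window for lab collection is 1-3 days prior to, or on, the day of prostatectomy".

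Other provisions bear on how the criterion works in practice. Section 5.3 (Registration process) has the coordinator "Verify patient eligibility worksheet is complete". It also has the required laboratory results sent in as source documents and lets the coordinator ask for more. Section 4.1.2 admits only men who have been recommended for radical prostatectomy and have chosen it. Section 4.2.13 excludes anyone with a condition that, "in the opinion of the investigator, would compromise the well-being of the subject" or would compromise the study.

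**The concern.** A platelet floor of 100 thousand is an understandable entry condition for men who are about to have major surgery, but the usual sense of that figure is per microlitre. Written per millilitre, the number is so low that it no longer acts as a limit.

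At stake is whether an operative safety criterion says what is applied. If staff use 100,000 per microlitre while the protocol says per mL, the written and applied criteria differ, and an auditor comparing a patient's count with the text of 4.1.6 would be checking against the wrong value. No estimate, test or power figure depends on this criterion.

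**Working it through.** The plan gives a limit and no calculation, so there is no derived figure to reproduce. The check is a unit conversion followed by a search for any other statement of the limit.

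**Inputs**

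- Limit as supplied (Section 4.1.6): 100k/mL = 100,000 per mL.
- Presumed intent: 100,000 per microlitre. This is an assumption: the same numeral with the unit changed. The documents do not state it.

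**Step 1: the limit as written**

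- 100,000 per mL / 1,000 microlitres per mL = 100 per microlitre.
- 100,000 per mL x 1,000 mL per L = 10^8 per L = 0.1 x 10^9/L.

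**Step 2: the presumed limit**

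- 100,000 per microlitre x 10^6 microlitres per L = 10^11 per L = 100 x 10^9/L.

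**Step 3: the gap**

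- 100 x 10^9/L divided by 0.1 x 10^9/L = 1,000.
- Counts from 0.1 to just under 100 x 10^9/L pass the written limit and fail the presumed one.
- A count of 50 x 10^9/L is 50 / 0.1 = 500 times the written limit.
- A count of 10 x 10^9/L is 10 / 0.1 = 100 times the written limit.

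**Step 4: does anything else supply the value?** Sections 5.2.3.1 and 11 name the test without a number or unit. Section 4.2.13 is discretionary and has no number. The eligibility worksheet named in Section 5.3 is not among the documents; Appendix II is only the registration form. So 4.1.6 stands alone.

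**Step 5: what still works in 4.1.6?** The second condition does not depend on the unit. A count that relies on transfusion or growth factors within the look-back period fails either way.

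**Step 6: could the unit be a reading error?** The supplied text points both ways.

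- Section 10.2.2 prints quantities that look like micro units with an m: "Genotyping PCR reaction (50 ml) will be done with 30-100 ng genomic DNA" and "0.2 mM of each primer, and 0.5 ml Phusion High-Fidelity DNA Polymerase". Whether that comes from the source or from PDF reading cannot be told.
- Section 10.5 keeps the micro sign in its reaction volumes (20 and 10 microlitres).
- Section 4.1 has no other micro unit against which to test 4.1.6.

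The question stays open on these documents.

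**The case against.** The strongest objection is that this may not be an error in the plan at all. Section 10.2.2 shows that apparent micro units can turn up as m in this text, and one intact micro sign in Section 10.5 does not prove that the sign survived everywhere. A reader might infer that any damage is confined to Section 10.2.2, so that 4.1.6 must be a genuine slip. The documents do not support that: symbols are inconsistent across Section 10 (10.5 keeps micro signs but prints temperatures without degree marks), and Section 4.1 offers no test case. This part of the objection stands, and the point is therefore conditional on the source document.

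The second objection is that the literal reading would hardly ever be applied. Staff would probably take the limit as per microlitre. The laboratory report is in the file at registration, so the check there is more than a completeness check. Section 4.1.2 puts a surgical recommendation ahead of the platelet criterion. Section 13.2.6.2 refers to pre-surgical blood counts and other tests required by surgical protocols, and the Study Calendar repeats the count. This also stands, and it makes counts such as 10 or 50 x 10^9/L largely theoretical. None of these provisions states a platelet number, however, so they lower the risk without correcting the text.

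Third, the worksheet may already carry the right unit. It was not supplied, so nothing can be said about it either way.

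**Conclusion.** The point holds as a low-severity unit correction, conditional on the source text. As supplied, 4.1.6 sets 0.1 x 10^9/L where 100 x 10^9/L was presumably meant, a factor of 1,000, and no other section states the limit. The conversion is exact. Two things are not established: that the source document also reads per mL, and that 100,000 per microlitre is the intended value. If the source reads per microlitre, the point falls away.

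A reader might go further and infer that men with very low platelet counts would be enrolled and taken to surgery. The documents do not support that, because the surgical recommendation, the submitted laboratory reports, the repeat counts and the investigator's discretion all stand in the way. Nor does the point touch the sample size of 57, the power statement or the analysis in Section 14.

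**What to change.** 1. Check the unit of 4.1.6 in the source document. If it reads per microlitre, no change is needed.
2. If it reads per mL, restate the criterion as a platelet count of at least 100,000 per microlitre (100 x 10^9/L), with the sponsor confirming the value. Leave the transfusion and growth-factor condition as it is.
3. Check that the eligibility worksheet uses the same value and unit, and change it only if it does not.

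The cost is one line of amendment wording and, if needed, one line on the worksheet. No extra test, visit or patient is involved.

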## 4.2 Exclusion criteria

Potential subjects who meet any of the following criteria will be excluded from participating in the study.

4.2.1 The use of any prior hormones including LHRH agonists, LHRH antagonists, antiandrogens such as bicalutamide, flutamide and nilutamide, and/or the use of 5-alpha reductase inhibitors, PC-SPES (or PC-x product), Megestrol Acetate, or estrogen containing nutraceuticals within 6 months of study treatment initiation.

4.2.2 Prior radiation therapy, immunotherapy, chemotherapy or other investigational therapy given for prostate cancer.

4.2.3 "Currently active" second malignancy other than non-melanoma skin cancers or non-muscle invasive transitional cell carcinoma of bladder. Patients are not considered to have a "currently active" malignancy if they have completed therapy and are now considered (by their physician) to be at less than 30% risk for relapse.

4.2.4 History of seizure or condition that may pre-dispose to seizure (including but not limited to prior stroke, transient ischemic attack, loss of consciousness within 1 year prior to randomization, brain arteriovenous malformation; or intracranial masses such as schwannomas and meningiomas that are causing edema or mass effect)

4.2.5 Have received treatment with any form of therapy with CYP17 inhibitory activity such as ketoconazole, aminoglutethemide, or an antiandrogen such as bicalutamide within 6 months of study treatment initiation.

4.2.6 Systemic corticosteroids within 6 months of enrollment

4.2.7 Active infection (eg, human immunodeficiency virus [HIV] or viral hepatitis)

4.2.8 Have uncontrolled hypertension; subjects with a history of hypertension are permitted in the study provided their blood pressure is controlled by anti-hypertensive therapy, at the discretion of the treating physician.

4.2.9 Have a known history of pituitary or adrenal dysfunction

4.2.10 Have clinically significant heart disease as evidenced by severe or unstable angina, myocardial infarction, symptomatic congestive heart failure, arterial or venous thromboembolic

events (e.g., pulmonary embolism, cerebrovascular accident including transient ischemic attacks), or clinically significant ventricular arrhythmias within 6 months prior to randomization

4.2.11 Have a history of gastric bypass surgery or severe malabsorption that may interfere with the absorption of the study agents

4.2.12 Be taking or require the use of prohibited medications as listed in Section 6.3.2.1

4.2.13 Have any condition that, in the opinion of the investigator, would compromise the well-being of the subject or the study or prevent the subject from meeting or performing study requirements

### **4.3 Inclusion of Minorities**

Men of all races and ethnic groups, English or non-English-speaking are eligible for this trial.

## **5 Registration**

### **5.1 General Guidelines**

All subjects who have been consented are to be registered in the OnCore Database. Eligible patients will be entered on study centrally at the Cleveland Clinic Taussig Cancer Institute by the Study Coordinator. Following registration, patients should begin protocol treatment on day (-28)  $\pm$  3 days which is set based on the scheduled surgery date. If a patient does not receive protocol therapy as scheduled following registration, the patient's registration on the study may be canceled. For those subjects who are consented, but not enrolled, the reason for exclusion must be recorded. The Study Coordinator should be notified of cancellations as soon as possible.

A subject who either prematurely discontinues from the study before completing 28 days of the treatment, prior to surgery, or for whom we are unable to obtain a tissue sample from, may be replaced at the discretion of the PI.

